6.3 Study Intervention Compliance

Study treatment consists of a single administration session administered by the study investigator.

6.4 Prior and Concomitant Medications

Concomitant medications are defined as medications taken any time after the start of dosing until discharge assessments. All concomitant medication, including blood and blood products, dietary supplements, and non-prescription drugs, will be listed at screening/baseline. Each entry will include the treatment's start date, treatment name (generic), reason for use, dosing regimen (dose and frequency of use), route of administration, and stop date (if applicable). Study subjects will be routinely questioned for changes in the administration of concomitant medication during the trial and changes should be updated from medical records as well.

7.0 STUDY INTERVENTION DISCONTINUATION

A premature discontinuation from study will occur when a subject who signed informed consent ceases participation in this study, regardless of circumstances, prior to completion of the protocol. Subjects can be prematurely discontinued from the study for one of the following reasons:

- Failure to meet inclusion/exclusion criteria before receiving first dose of study drug has been administered
- Death
- Significant safety event that in the opinion of the Investigator warrants discontinuation. Raziel will attempt to follow up all subjects for safety.
- Lost to follow-up after every attempt has been made to contact the subject, including sending a registered letter
- Subject withdraws consent

The Principal Investigator and the Institutional Review Board/Ethics Committee (IRB/EC) reserve the right to prematurely terminate the study in the interest of subject safety and welfare. The Sponsor reserves the right to prematurely terminate the study at any time for administrative reasons.

8.0 STUDY ASSESSMENTS AND PROCEDURES

8.1 Medical History

A medical history will be obtained at screening. Subject's medical history should be fully documented to confirm study eligibility. Medical history must include, but not limited to, past and present medical conditions, concomitant non-drug treatments, and hypersensitivity to drugs.

8.2 Height

Height will be measured at screening. It will be reported in centimeters. A subject's height together with weight will be used to calculate a subject's BMI.

8.3 Weight

Body weight will be measured at screening, baseline (day 1) and at the study visit Day 28 and study visit Day 84. Weight will be reported in kilograms (kg). A subject's weight at screening together with height will be used to calculate a subject's BMI.

8.4 Pregnancy Tests

A serum (β -hCG) pregnancy test will be administered to females of childbearing potential at screening and a urine pregnancy test will be administered at baseline prior to dosing. Additional serum pregnancy tests will be done at any time during the study (up to Day 84), if pregnancy is suspected. Urine pregnancy test will be done to females of childbearing potential on Day 84.

8.5 Complete Physical Examination

The Investigator (or medically qualified nominee) will perform a complete physical examination at screening and on Day 7 and Day 84 visit.

8.6 Clinician-Chin Assessment Tool (C-CAT)

SMF ratings using the C-CAT will be conducted by a fixed and well-trained Investigator at screening and baseline (Day 1) and at study visits on Days 28, 56, and 84 to assess the change in SMF severity before and following treatment.

The C-CAT score will be based on the Investigator’s clinical evaluation of the subject in the Frankfurt horizontal plane. Clinical evaluation will include palpation of the chin and neck area, anterior, oblique and profile views of the chin and neck, and observation of pronation, supination, and lateral movement of the head. The score will be determined using the rating scale definitions. The score will be recorded as a whole number. At screening, the score will be used in conjunction with inclusion criteria.

The C-CAT is defined below. The scale is A 5-point scale (scored 0-4).

The grading system categorizes 3 aspects of submental chin fat: bulge, (size of the submental fat bulge) neck (extension of the bulge into the neck, downward and lateral) and jawline (the appearance of the jawline, presence of fat and definition of the jawline).

Each grade contains a description and a line drawing. Each grade is distinct and non-overlapping.

A comprehensive training guide with representative photographic examples and line drawing to each grade will be provided to the study center sites for training and visual comparison.

Table 3 Clinician Chin Assessment Tool (C-CAT)

Clinician Chin Assessment Tool (C-CAT)		
Score	Line Drawing	Description
0		
 No bulge under chin No fat in the neck No fat along the jawline; jawline is visible and well defined
1		
 Barely visible bulge, only visible in lateral and oblique views, not visible in frontal view No fat in the neck No fat along the jawline; jawline is visible and well defined
2		
 Small but visible bulge, visible from all angles (lateral, oblique and frontal) No fat in the neck Fat may be present in the jawline; jawline is still visible and defined
3		
 Noticeable bulge; visible in all angles (lateral, oblique and frontal) Fat extends downward into the neck but does not extend to the laryngeal prominence (mid-neck) Fat may extend laterally along the jawline; jawline is visible but may be poorly defined
4		
 Very noticeable bulge, visible in all angles (lateral, oblique and frontal) Fat extends down the neck to the laryngeal prominence and may extend beyond Fat extends laterally along the jawline; jawline is poorly defined and may be indistinguishable from the neck

8.7 Subject – Self-Chin Assessment Tool (S-CAT)

SMF ratings using the S-CAT will be conducted by the subject at screening and baseline (Day 1) and at study visits on Days 28, 56, and 84 to assess the change in SMF area following treatment.

The scale has 5 grades from 0 to 4. Each grade utilizing line-drawings and descriptors to identify 5 unique and non-overlapping grades.

The chin fat is categorized by the following features: bulge (size of the fat bulge) neck (extension of the bulge downward and laterally into the neck) and jawline (presence of fat and definition of the jawline).

Self evaluations should be made sitting in an upright position with the chin at a right angle (as illustrated in the line drawings). Mirrors will be used to see the chin, neck and jawline from both front and side views.

A comprehensive training guide with representative photographic examples and line drawing to each grade will be provided to the subjects.

Table 4 Self Chin Assessment Tool (S-CAT)

Self Chin Assessment Tool (S-CAT)		
Score	Line Drawing	Description
0		
 No bulge under chin No fat in the neck No fat along the jawline; jawline is visible and well defined
1		
 Barely visible bulge, only visible from the side, not visible in the straight ahead view No fat in the neck No fat along the jawline; jawline is visible and well defined
2		
 Small but visible bulge, visible from the front and sides views No fat in the neck Fat may be present in the jawline; jawline is still visible and defined
3		
 Noticeable bulge; visible from the front and side views Fat extends downward into the neck but does not extend to the Adam's Apple (mid neck) Fat may extend laterally along the jawline; jawline is visible but may be poorly defined

8.8 Magnetic Resonance Imaging (MRI)

The purpose of the MRI exam is to evaluate whether the additional treatments (i.e., lidocaine, Celecoxid, Zyrtec etc.) affects the fat reduction following treatment of RZL-012. MRI exams will be conducted in imaging centers close to selected clinical sites.

MRI will be conducted at screening in order to establish a baseline value for assessment of treatment efficacy. Post-treatment period MRI will be completed within 84 days (\pm 14 days) after the treatment session.

Quantitative measurements such as fat volume of the SMF area will be used as an objective parameter for measurement of SMF reduction following treatment.

Sagittal 2D and 3D images of the head and neck (chin area) will be obtained using 1.5 Tesla machine (General Electric, Siemens, Phillips or other). For each MRI visit, the total imaging time is expected to be approximately thirty (30) minutes.

During the imaging, subjects will be positioned in Head first Supine recumbent. Images in the sagittal plane across the entire submental region will be collected using an appropriate MR sequence to minimize the effects of air cavities, dental implants, and amalgam on the resultant MR image. This imaging approach will generate a 2D and 3D image data set that allows for the quantification of the SMF volume in several slices covering the treatment area. In the follow up MRI exam, slices will be positioned as similar as possible to the first MRI exam.

Images should be saved in a DICOM format and include the date completed and subject's screening number to be transferred home the Sponsor's request for central analysis.

Submental volume analysis will be performed by computer-assisted tools and calculation of submental volume will be completed prior to dosing and after treatment.

8.9 2-D Standardized Photography

Standardized photography (2-dimensional) of the face (SMF area) will be conducted at screening and on study visits Day 2, Day 4, Day 7, Day 14, Day 21, Day 28, Day 56, and Day 84.

Photographs will be taken with a digital camera according to photography standards in dermatology surgeries for the face/neck area (see Appendix A).

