1.0 PROTOCOL SUMMARY

1.1 Protocol Synopsis

Study Title	An Open Label Phase 2 Study to Evaluate the Effects of a Local Anesthetic, Anti-inflammatory Medications and Compression Garments on RZL-012-Induced Adverse Events (RZL-012-SMF-SWMTG-P2US-001)
Phase	Phase 2
Study Drug	RZL-012
Study Objectives and Endpoints	
Primary Objective:
 
 To compare the benefits of lidocaine, methylprednisolone, Celecoxib +cetirizine or compression dressings on RZL-012-induced adverse events 
Secondary Objectives:
 
 To test the safety and tolerability profile of combining lidocaine, methylprednisolone, Celecoxib + cetirizine or compression garment with RZL-012 
Primary Endpoint: Safety and tolerability profile of combining lidocaine, methylprednisolone, Celecoxib +cetirizine or a compression garment with RZL-012
 
Exploratory Endpoints:
 
 Proportion of subjects who have at least a 1-grade improvement in the C-CAT on Day 84 versus baseline in subjects receiving RZL-012 alone or in combination with other medications. Proportion of subjects who have at least a 1-grade improvement in the S-CAT on Day 84 versus baseline in subjects receiving RZL-012 alone or in combination with other medications. Proportion of subjects who have at least a 1-grade improvement in both C-CAT and S-CAT on Day 84 versus baseline in subjects receiving RZL-012 alone or in combination with other medications. Proportion of subjects who have at least a 2-grade improvement in both C-CAT and S-CAT on Day 84 versus baseline in subjects receiving RZL-012 alone or in combination with other medications. Changes in SMF volume measured by MRI scans on Day 84 versus baseline in subjects receiving RZL-012 alone or in combination with other medications. Satisfaction in subjects receiving RZL-012 alone or in combination with other medications.

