	
4. RZL-012 and Celecoxib and cetirizine (200 mg Celecoxib BID and 10 mg cetirizine BID on Days 1, 2, 3, 4, 5 and 6)
 
5. RZL-012 + sling/pressure garment (until Day 6)
 
In the first stage of the study, 5 subjects will be randomized into each of the treatment groups. Study outcomes will be assessed up to one week thereafter to determine the need to modify additional study treatments. Subsequently up to 10 additional subjects will be randomized into each of the treatment groups for the second stage of the study.
 
For each subject, the study will consist of a screening period, baseline period in which subjects will receive a single treatment session of RZL-012 and a follow-up period. RZL-012 will be administered during a single treatment session via multiple injections into the submental area under the chin. Subjects will thereafter be monitored for safety and efficacy for at least 84 days.
 
Each subject will be treated with the same dose of RZL-012 :
 
• RZL-012 (concentration of injected solution 50 mg/mL RZL-012) of 7.5 mg/0.15 mL/injection point that results in a total dose/volume of 240±30mg mg/4.8±0.6 mL RZL-012, 
Each subject will receive additional study treatments in accordance with the treatment group to which the subject is randomized.
 
Screening Period:
 
Subjects will undergo screening within 28 days prior to being treated with RZL-012. During the screening period subjects will be assessed for study eligibility by evaluation of subjects' SMF using S-CAT , C-CAT, biochemistry blood tests, MRI, 2D photography. ECG will also be conducted during the screening visit. Following completion of study procedures (including MRI), subjects will be randomized in order for the PI to administer subjects with the Rx prescription, if appropriate (i.e., Celecoxib / cetirizine).
 
Day 1/Baseline:
 
At Baseline visit, subjects will be given with their randomized medication if appropriate. Subjects will receive a single multi-injection treatment of RZL-012 on Day 1. AEs will be recorded. Subjects will be asked about their pain levels using VAS. Additional medications/treatments, will be given according to its instructions for use.
 
Day 1-Day 84 Follow-Up Period
 
Subjects will return to the site for study visits on Days 2, 4, 7, 14, 21, 28, 56 and 84 for efficacy and safety assessments.
 
For subjects having unresolved AEs on Day 84, an unscheduled visit will be set 6-8 weeks after Day 84 to verify the resolution of the AE. On that visit, follow up of using photographs C-CAT and S-CAT will also be conducted.
 
Subjects will be advised to continue their regular diet and physical activity during the study.
 
Safety assessments include vital signs, ECG, AEs severity assessment, and treatment area evaluation. Treatment area evaluations including, but not limited to evaluation of edema, bruising, dysphasia, dysphonia, erythema, dyspigmentation, induration, numbness, pain, paresthesia, pruritus, skin ulceration and necrosis, injury to the marginal mandibular nerve, vascular and nerve injury and tissue damage to nearby vulnerable anatomic structures. Specifically, degree of swelling severity will be assessed as a function of time and in each visit Subjects will be asked about their pain levels using VAS. Pain at injection site will not

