--	--

	be recorded as an AE but the information regarding pain will be obtained from the VAS scores completed by the subject. Concomitant medications will be recorded.
Sample Size	Up to 75 subjects (5 in each treatment group in stage 1 of the study and up to 10 subjects in each treatment group in stage 2 of the study).
Study Population	Adult volunteers age 18 to 65 years who have consented to participate in this study.

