
Statistical Analysis
	
All measured variables and derived parameters will be listed individually and, if appropriate, tabulated by descriptive statistics.
 
For categorical variables, summary tables will be provided giving sample size, absolute and relative frequency, and 95% confidence interval (CI) for proportions by study arm.
 
For continuous variables, summary tables will be provided giving sample size, arithmetic mean, standard deviation, coefficient of variations (CV%), median, minimum and maximum, and 95% CI for means of variables by study arm.
 
Primary endpoint and exploratory endpoints will be analyzed in descriptive manner.
 
The data will be analyzed using the SAS version 9.4 (SAS Institute, Cary North Carolina).

Study Duration
	
It is planned that each subject will participate in the study for 4 months, which comprises a screening period, baseline/treatment period, and follow up period.

Study Centers
	
6 clinical centers

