9.0 STATISTICAL CONSIDERATIONS

9.1 Sample Size Determination

A total of 75 subjects will be included in the study. All subjects will be treated with RZL-012. Each 15 subjects will be randomized into each of the treatment groups.

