9.3 Endpoints Analyses

All measured variables and derived parameters will be listed individually and, if appropriate, tabulated by descriptive statistics.

For categorical variables, summary tables will be provided giving sample size, absolute and relative frequency, and 95% confidence interval (CI) for proportions by study arm.

For continuous variables, summary tables will be provided giving sample size, arithmetic mean, standard deviation, coefficient of variations (CV%), median, minimum and maximum, and 95% CI for means of variables by study arm.

Primary endpoint and exploratory endpoints will be analyzed in descriptive manner.

The data will be analyzed using the SAS version 9.4 (SAS Institute, Cary North Carolina).

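### The MRI is meant to show whether the added treatments change RZL-012 fat reduction, but the analysis plan gives only by-arm summaries and no estimate against Group 1

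*Combined protocol and SAP*

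**What the plan says.** Section 8.8 states why the scans are done: to "evaluate whether the additional treatments (i.e., lidocaine, Celecoxid, Zyrtec etc.) affects the fat reduction following treatment of RZL-012". The matching exploratory endpoint in the synopsis is "Changes in SMF volume measured by MRI scans on Day 84 versus baseline in subjects receiving RZL-012 alone or in combination with other medications". Group 1 in section 4.1 is a concurrent randomized arm that receives RZL-012 with no added treatment.

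For continuous variables, section 9.3 plans descriptive statistics with "95% CI for means of variables by study arm". It adds, as does the synopsis, "Primary endpoint and exploratory endpoints will be analyzed in descriptive manner". Section 9.4 covers safety only. No section plans a difference or ratio against Group 1 for MRI volume, a model, or a baseline adjustment.

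A baseline value exists: "MRI will be conducted at screening in order to establish a baseline value for assessment of treatment efficacy". It is obtained before allocation: "Following completion of study procedures (including MRI), subjects will be randomized".

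On size, section 9.1 says "Each 15 subjects will be randomized into each of the treatment groups". The synopsis has 5 per group in stage 1 and "up to 10 subjects in each treatment group in stage 2 of the study", so 15 per arm is the maximum.

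**The concern.** Whether an added treatment affects fat reduction is a question about add-on versus no add-on. Its natural answer is the difference between each combination arm and Group 1, with an interval. The planned output instead sets each arm's mean change against zero.

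An add-on arm could lose a good part of the RZL-012 effect and still have an interval that excludes zero. A reader could then conclude that the add-on leaves efficacy intact, although the table does not support that. Sections 1.3.2 and 4.3 look ahead to Phase 3, so such a conclusion could carry weight.

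**Working it through.** **The plan's own figure.** 5 arms × (5 + 10) = 75, as in section 9.1. The protocol gives no SD, target difference, margin or power for MRI volume, so there is nothing further to reproduce.

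**Inputs**
- Arm size: 15 evaluable, the best case. Section 8.8 places the scans near selected sites; if that limits who is scanned, n is lower.
- SD: 14.9 percentage points, from the Phase 2a high-dose result of −22.2% ± 14.9 (section 1.2.2.1, N = 10). This is an assumption, because the ± is not labelled. Range shown: 10 to 20.
- Size of the effect: 14.9 points (Phase 2b high dose, 270 mg) or 22.2 points (Phase 2a high dose, average 158.5 mg). The dose here is 240 ± 30 mg.

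**Is the ± an SD?** The Phase 2a p-values in section 1.2.2.1 give mixed signals.
- High dose v placebo (−22.2 v −0.4, N = 10 each), read as SD: pooled SD = √((14.9² + 13.9²)/2) = 14.41; t = 21.8/(14.41 × √(2/10)) = 3.4, p about 0.003. This fits the stated p < 0.05.
- Low dose v placebo (−10.6 ± 14.5, N = 8, v −0.4 ± 13.9, N = 10), read as SD: pooled SD 14.17; t = 10.2/(14.17 × √(1/8 + 1/10)) = 1.5, p about 0.15. The stated value is 0.67.
- Read as standard errors, the low dose gives t = 10.2/√(14.5² + 13.9²) = 0.5 (p about 0.62), but the high dose gives t = 21.8/√(14.9² + 13.9²) = 1.1 (p about 0.30).

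Neither reading fits both results, which is why a range of SDs is needed.

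**What the planned table shows.** By-arm half-width = t(14) × SD/√15 = 2.145 × 14.9/√15 = 8.25 points.

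**What the question in 8.8 needs.** Half-width of a difference from Group 1, variance pooled over five arms = t(5n − 5) × SD × √(2/n).

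| n per arm | SD | Calculation | Half-width | % of 14.9 | % of 22.2 |
|---|---|---|---|---|---|
| 15 | 14.9 | 1.994 × 14.9 × √(2/15) | ±10.9 | 73% | 49% |
| 15 | 10 | 1.994 × 10 × √(2/15) | ±7.3 | 49% | 33% |
| 15 | 20 | 1.994 × 20 × √(2/15) | ±14.6 | 98% | 66% |
| 12 | 14.9 | 2.004 × 14.9 × √(2/12) | ±12.2 | 82% | 55% |
| 10 (stage 2 alone) | 14.9 | 2.014 × 14.9 × √(2/10) | ±13.4 | 90% | 60% |

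So at 15 per arm, an observed difference of zero would still leave a loss of up to about 10.9 points open.

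**Why the by-arm intervals are a poor guide**
- An arm that keeps 60% of a 14.9-point reduction has mean 0.6 × 14.9 = 8.9. Its interval, 8.9 ± 8.25, excludes zero although 40% has been lost.
- Two arms whose intervals just touch differ by 2 × 8.25 = 16.5 points. The standard error of the difference is 14.9 × √(2/15) = 5.44, so t = 16.5/5.44 = 3.03 and p = 0.005 on 28 df. Overlapping intervals therefore do not mean that there is no difference.

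**What the baseline covariate could gain.** With correlation r between screening volume and percent change, the half-width is about 1.995 × 14.9 × √(2/15) × √(1 − r²). This gives ±10.9 for r = 0, ±10.4 for 0.3, ±9.4 for 0.5 and ±7.8 for 0.7. The protocol gives no value of r, so the gain may be nil.

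**Multiplicity.** Simultaneous Dunnett intervals for the four contrasts would use the critical value 2.499: 2.499 × 5.44 = ±13.6 points.

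**The case against.** The strongest reply is that no stated objective goes unmet. The objectives in section 3.1 concern adverse events and safety. MRI volume is exploratory, the only contrast its endpoint names is Day 84 against baseline, and the comparative wording comes from one sentence in an assessment section. A descriptive plan is a legitimate choice in a small open-label Phase 2 study that makes no power claim. The table will contain n, mean and SD for every arm including Group 1, so anyone can work out a crude difference and its interval. The primary objective is comparative too and has the same by-arm plan; modelling only an exploratory endpoint would treat it more fully than the main question.

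Most of this stands, and it limits the weight of the point. A derivable difference is nevertheless not a pre-specified one: it is not baseline-adjusted and may not be reported. The parallel gap for the primary objective is a separate matter and does not close this one. Estimation with intervals is compatible with a descriptive analysis.

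A reader might also infer that a log-scale ratio model is required. The figures do not support that. With SDlog = 0.149/0.851 = 0.175 and no baseline correlation, the half-width is 1.995 × 0.175 × √(2/15) = 0.1275, and the loss left open is 0.851 × (e^0.1275 − 1)/0.149 = 78% of the 14.9-point effect. With SDlog = 0.149/0.778 = 0.1915 it is 86%. The plain difference leaves 73%. The scale is a matter of choice.

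**Conclusion.** The point holds as a minor one. Section 8.8 asks a between-arm question, the design supplies the comparator, and section 9.3 and the synopsis plan no estimate that answers it. The uncertainty left unshown is about ±10.9 points, 73% of the 14.9-point Phase 2b effect or 49% of the 22.2-point Phase 2a effect. This rests on 15 evaluable per arm and an SD of 14.9, which fits only one of the two Phase 2a p-values.

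Two stronger conclusions might be drawn, and the documents support neither. One is that the trial or its MRI analysis is invalid: the endpoint is exploratory, the analysis is openly descriptive, and a crude contrast can be recovered from the planned table. The other is that a stage 2 contrast would settle the question if an add-on is changed after stage 1: at about ±13.4 points for 10 v 10 it can only be descriptive. Sample size remains the main limit, and no analysis choice removes it.

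**What to change.** In section 9.3, and in the synopsis to match, add for Day 84 MRI volume change:
- each of Groups 2 to 5 minus Group 1 with a 95% CI, from one model with arm and screening MRI volume as covariate; percent change or log scale is for the sponsor to choose, in advance;
- a label of exploratory estimation without hypothesis tests, noting that the four intervals share one control and are not adjusted for multiplicity;
- a statement that neither a wide interval nor a by-arm CI that excludes zero is evidence that the effect is preserved;
- a rule that, if an added treatment is modified after stage 1, that arm's two stages are not pooled without saying so, and that any stage 2 contrast is descriptive only.

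The cost is one model, one table and one degree of freedom, with no extra subjects or scans. Adjustment may gain no precision if screening volume is unrelated to change, and the reading of efficacy becomes more cautious.
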